## 4. STUDY DESIGN

[figure not shown]
### 4.1. GENERAL DESCRIPTION

SEP380-303 is a 12-month open-label safety extension study to evaluate the long-term safety, tolerability, and effectiveness of SEP-4199 CR 200-400 mg/day in the treatment of subjects with bipolar I depression who previously completed a lead-in study of SEP-4199 CR.

The study will consist of a 12-month open-label flexible-dose treatment period, and a safety follow-up period, as shown in the following figure. There are 15 scheduled visits, including a Baseline visit, 13 visits during the open-label treatment period, and 1 safety follow-up visit 7 ( $\pm 2$ ) days after the last dose of study drug. If necessary, subjects may return to the clinic at any time for an unscheduled visit (see [Figure 1](#)).

Subjects who meet the entry criteria will transition immediately at the End of Treatment (EOT) visit from Study SEP380-301. The EOT visit from studies SEP380-301 will generally serve as the Baseline visit for the present study. Informed consent will be obtained from all subjects before any study procedures are performed for the present study.

A study schematic is presented in Figure 1.

**Figure 1: Study schematic – All Subjects**

Note: All subjects are to take SEP-4199 CR 200 mg beginning on Day 1, the day following Baseline (Visit 1E). There is an extra visit for Japan (Visit1EJ) on Day 1 (evaluates ECG).

Abbreviations: BL = Baseline; CR = controlled release; EOT = end of treatment. V = visit; E = extension; W = Week; M = Month

## 4.2. METHOD OF ASSIGNING SUBJECTS TO TREATMENT GROUPS

There is an open-label study and no randomization planned in this study. All subjects will receive flexible dosing with SEP-4199 CR 200 mg/day or 400 mg/day during the 52 weeks of treatment.

## 4.3. BLINDING

This is an open-label study. All subjects will receive flexible dosing with SEP-4199 CR 200 mg/day or 400 mg/day.

## 4.4. DETERMINATION OF SAMPLE SIZE

All subjects who complete the 6-week double-blind treatment period in Study SEP380-301 are eligible to enrol in the current study. Assuming a completion rate of 85% in the SEP-4199 CR Study SEP380-301 and 80% rollover rate of completers from that study to the current extension study, it is estimated that approximately 355 subjects will be enrolled in this study. Due to early termination of the Study SEP380-301, there are 64 subjects were enrolled in this study.

## 4.5. CHANGES IN THE CONDUCT OF THE STUDY

The first subject was enrolled on ddmmmm2022 under protocol Version 1.00 (dated 20MAY2021). Additional protocol versions and amendments are listed below.

- Protocol version 2.00 (7SEP2021); Amendment 1.00 (7SEP2021).

## 4.6. SCHEDULE OF EVENTS

Schedule of events can be found in Section 1, Table 2 of the Clinical Study Protocol (CSP). This table is also included in [APPENDIX 7](#) of the SAP.

## 4.7. CHANGES TO ANALYSIS FROM PROTOCOL

Because of the small sample size due to study early termination, the following main changes will be made for this study:

- Only 2 treatment groups will be formed based on a subject's previous participation in the lead-in study of SEP-4199 CR (SEP-SEP: previously randomized to any SEP-4199 CR dose group and PBO-SEP: previously randomized to placebo).
- No subgroup summaries will be performed.
- No summaries using Follow-up population will be performed.
- Except for PWC, follow-up period summaries will not be performed, PWC will be summarized by Safety population.
- AE will not be summarized by high-level term (HLT).
- No Kaplan-Meier curves will be plotted for time to discontinuation and time to the earliest onsets of the selected AESI. The Kaplan-Meier estimation will also not be performed.
- To be consistent with AIMS and BARS, MSAS will be summarized by total score.

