15.4.3.1. Adverse Events

All AEs will be coded using the Medical Dictionary for Regulatory Activities (MedDRA). Information on the format and version of the coding dictionary is provided in the DMP.

A treatment-emergent adverse event (TEAE) (hereafter referred to as AE) is an adverse event with onset data on or after the first day of the open-label treatment period through 7 days after study drug discontinuation (14 days for serious adverse events). The start of the open-label treatment period is defined as the first dose day for subjects previously randomized to placebo group and the OL Baseline visit date for subjects previously randomized to SEP-4199 CR groups.

The incidence of AEs, SAEs, and AEs leading to discontinuation due to AEs (or SAEs) will be summarized by analysis group (by presenting the number and percentage of subjects with one or more AEs in each category). The number and proportion of subjects with one or more AEs within a system organ class (SOC) and by preferred term (PT) will be presented by analysis group as well. The incidence of AEs (by preferred term, grouped by SOC) will also be summarized by severity, by the relationship to study medication, by the action taken regarding the study medication, as well as by the outcome. In addition, AEs will also be summarized by SOC, high-level term (HLT), and PT by presenting the number and percentage of subjects within each AE category.

The incidence of AESI, including but not limited to hyper-prolactinemia related AEs, will be summarized for overall and by gender as appropriate. For selected AESI, Kaplan-Meier curves will be plotted by analysis group for time to the earliest onsets. AEs associated with EPS will be summarized by analysis group.

Incidence of post-treatment adverse events (defined as an AE with a start date after the date of last dose of study drug through the last contact/visit in the follow-up period) will be summarized separately for subjects in the follow-up population.

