#### 3.1.1. PRIMARY OBJECTIVE

The primary objective of the current study is to evaluate the long-term safety and tolerability of treatment with SEP-4199 CR 200-400 mg/day, as reflected in rates of adverse events (AEs), discontinuations due to an AE, serious AEs (SAEs), and adverse events of special interest (AESI).

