## **3.2. STUDY ENDPOINTS**

### **3.2.1. PRIMARY ENDPOINTS**

- The incidence of overall AEs, discontinuation due to AEs, and SAEs

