## 15. STUDY MEDICATION EXPOSURE

Unless otherwise specified, the study medication exposure summary tables will include the following columns: PBO-SEP, SEP-SEP, and ALL EXT (all rollovers from SEP380-301).

Exposure to OLE study medication data will be summarized for the Safety Population by the actual treatment group.

The date/time of first dose of OLE study drug and the date/time of last dose of OLE study drug will be respectively derived as the earliest ("Date Dosing Started" & "Time Dosing Started") pair and the latest ("Date Dosing Ended" & "Time Dosing Ended") pair as collected on the "Study Drug Administration / Drug Accountability" CRF form. The start and end dates/times from blister cards with the number of tablets dispensed equal to the (number of tablets returned + number of tablets reported lost) are excluded from the derivation.

Duration of exposure (in days) will be summarized both as a continuous variable for the OLE treatment period and categorically:

- Number and percentage of subjects with OLE study drug exposure  $\geq 1, \geq 14, \geq 30, \geq 60, \geq 90, \geq 120, \geq 150, \geq 180, \geq 210, \geq 240, \geq 270, \geq 300, \geq 330$ , and  $\geq 360$  days;
- Number and percentage of subjects with OLE study drug exposure for 1 - 13, 14 - 29, 30 - 59, 60 - 89, 90 - 119, 120 - 149, 150 - 179, 180 - 209, 210 - 239, 240 - 269, 270 - 299, 300 - 329, 330 - 359, and  $\geq 360$  days.

Total person-years of exposure to OLE study medication will be calculated for each actual treatment sequence and overall for all subjects in the Safety Population.

Mean daily dose and modal daily dose will be calculated for the entire OLE treatment period and summarized.

The number of days that a subject received the CR 200 mg/day dose level, and the CR 400 mg/day dose level during the OLE treatment period will be summarized for the Safety Population both as a continuous variable and categorically:

- Number and percentage of subjects with exposure to a particular dose level for 1 - 13, 14 - 29, 30 - 59, 60 - 89, 90 - 119, 120 - 149, 150 - 179, 180 - 209, 210 - 239, 240 - 269, 270 - 299, 300 - 329, 330 - 359, and  $\geq 360$  days.

Duration of exposure since SEP380-301 first dose (in days) will be summarized as a continuous variable for the Safety Population by the actual treatment group.

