Listings will be provided for all AEs, study medication-related AEs, severe AEs, serious AEs, AEs leading to discontinuation from the study, AEs leading to death, and AEs of special interest (AESI). A listing of SEP380-301 events (pre-treatment events and AEs) present in the SEP380-303 database will also be presented. When complete event start date and complete event end date are available, duration of AEs from SEP380-301/303 and pre-treatment events from SEP380-301 will be calculated as: event end date – event start date + 1. Duration will be presented in data listings.

For all summaries, each subject will be counted only once within each category (e.g., an AE type, a severity level, a relationship category, a SOC, and a PT). If not otherwise specified, all summaries will present the number and percentage of subjects as well as the number of events. For summaries by SOC and PT, AEs will be sorted by SOC based on the internationally agreed order (see [APPENDIX 4](#)) and then by PT in decreasing frequency in the “ALL EXT” column. For summaries by SOC, and PT, AEs will be sorted by SOC based on the internationally agreed order and then by PT in decreasing frequency in the “ALL EXT” column.

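### AEs, SAEs, AE discontinuations and AESI are reported as n (%) and event counts with no measure that allows for unequal follow-up, and SAP 4.7 removes the protocol's only such analysis, for selected AESI, without a replacement

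*SAP*

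**What the plan says.** SAP 3.1.1 sets the primary objective as long-term safety and tolerability, "as reflected in rates of adverse events (AEs), discontinuations due to an AE, serious AEs (SAEs), and adverse events of special interest (AESI"). SAP 3.2.1 gives the primary endpoints as "The incidence of overall AEs, discontinuation due to AEs, and SAEs"; AESI incidence sits under other safety endpoints in SAP 3.2.2.

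Protocol 15.4.3.1 summarises AEs, SAEs and AEs leading to discontinuation "by presenting the number and percentage of subjects with one or more AEs in each category". Its one time-to-event analysis of AEs is for AESI: "For selected AESI, Kaplan-Meier curves will be plotted by analysis group for time to the earliest onsets".

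SAP 4.7 gives small sample size after early termination as the reason for several changes, among them "No Kaplan-Meier curves will be plotted for time to discontinuation and time to the earliest onsets of the selected AESI". It continues: "The Kaplan-Meier estimation will also not be performed". SAP 18.1 then states that, unless specified otherwise, "all summaries will present the number and percentage of subjects as well as the number of events". Sections 18.1.1 to 18.1.4 define no rate per person-time and no time-to-event measure.

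SAP 15 does provide for exposure: "Total person-years of exposure to OLE study medication will be calculated for each actual treatment sequence", together with exposure categories running from 1-13 days to 360 days or more. SAP 10 tabulates discontinuation by visit and group. Person-years are not named as the denominator of any AE rate.

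**The concern.** This is a 12-month study whose objective is expressed as rates. Early leavers are not replaced (Protocol 13.1), and the exposure and discontinuation tables make room for follow-up of very different lengths. In an n/N table, a subject who leaves event-free at Week 2 counts the same as one who is event-free for a year. The percentage therefore describes what was seen over whatever follow-up occurred, and is not a 12-month risk.

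The gap matters most for the AESI. Some listed events need time to appear: Protocol 12.1.3 describes amenorrhea as at least three months without menses, and also lists fractures, osteoporosis and osteopenia. A subject who leaves at Week 2 cannot show on-study amenorrhea of that length but stays in the denominator. This is the category for which the protocol had planned Kaplan-Meier curves.

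Small sample size makes any estimate imprecise. It does not correct a percentage for early departure, so the reason given in SAP 4.7 does not by itself justify having no replacement.

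**Working it through.** No figure in the plan bears on this point. The only computed figure is the planned enrolment of about 355 (85% lead-in completion, 80% rollover). It inverts to a lead-in size of 355/(0.85 × 0.80) ≈ 522, which the documents do not give and which plays no part below.

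**Inputs.** Planned follow-up is 12 months (Protocol 7.1), and 64 subjects were enrolled (SAP 4.4). Event risk, dropout and event timing are not in the documents, so the values below are assumptions. Dropout means any end of follow-up before month 12, independent of the event.

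**Expected crude percentage with constant hazards.** Let p be the true 12-month risk and d the dropout by 12 months, with λ = −ln(1−p) and μ = −ln(1−d). Then

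expected n/N = λ/(λ+μ) × [1 − exp(−(λ+μ))].

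For p = 20%, λ = 0.223 per year:

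| d | μ | λ/(λ+μ) | 1 − exp(−(λ+μ)) | Expected n/N | Ratio to 20% |
|---|---|---|---|---|---|
| 20% | 0.223 | 0.500 | 0.36 | 18.0% | 0.90 |
| 40% | 0.511 | 0.304 | 0.52 | 15.8% | 0.79 |
| 60% | 0.916 | 0.196 | 0.68 | 13.3% | 0.67 |
| 70% | 1.204 | 0.156 | 0.76 | 11.9% | 0.59 |

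The ratios are similar for true risks of 5% to 30%.

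**If all events occur in the first 2 months.** Take λ = 0.223 × 6 = 1.339 per year, acting for 1/6 year. Expected n/N is then 19.2% at 40% dropout and 18.6% at 60%, a shortfall of (20 − 19.2)/20 = 4% and (20 − 18.6)/20 = 7% of the true risk.

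**Between columns, same true 20% risk, constant hazards.**

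- Dropout 40% and 40%: 15.8% and 15.8%, no distortion.
- Dropout 30% and 50%: 16.9% and 14.6%.
- Dropout 20% and 60%: 18.0% and 13.3%.

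**Is a censoring-aware estimate feasible at N = 64?** In 4,000 simulated studies with a true risk of 20%:

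| Dropout | Mean 1−KM at 12 months (SD) | Mean crude n/N (SD) | First events per person-year (true 0.223) |
|---|---|---|---|
| 40% | 20.1% (5.8 points) | 15.9% (4.6 points) | 0.227 |
| 60% | 19.8% (6.4 points) | 13.2% (4.2 points) | 0.224 |

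Both measures are close to the true value. In smaller groups (sizes of 43 and 21 are illustrative; the documents give no split) the SD of 1−KM at 40% dropout is 7.0 and 10.1 points.

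**Limit of the person-year rate.** Suppose the risk is 20%, all events fall in the first 2 months at a mean of 1 month, and two groups are followed for 0.4 and 0.8 years. Crude n/N is 20% in both. Person-years at risk per subject are 0.2 × 1/12 + 0.8 × 0.4 = 0.337 and 0.2 × 1/12 + 0.8 × 0.8 = 0.657. The rates are 0.2/0.337 ≈ 59 and 0.2/0.657 ≈ 30 per 100 person-years, a false twofold difference.

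**The case against.** The strongest reply is that the SAP does what a small descriptive study should do. It tests no hypothesis, discloses the change in the right section with a reason, and never calls its percentages 12-month risks. Protocol 15.4.3.1 itself defines incidence as number and percentage of subjects. Event counts, person-years by group, discontinuation by visit and full AE listings are all provided, so a reader can form events per person-year. At 40% dropout, the bias of 4.2 points (20 − 15.8) is smaller than the 5.8-point SD of the Kaplan-Meier estimate. A person-year rate can itself mislead when events cluster early, as shown above.

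Much of this stands, and it limits what can be claimed. The do-it-yourself rate is not a full substitute. Event counts include repeats, person-years run to the last dose and not to the first event (SAP 15.1), and the severity and relationship summaries omit event counts (SAP 18.1.1.1 and 18.1.1.2).

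A reader might infer three stronger things that the documents do not support:

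- **That SAP 4.7 took a censoring-aware analysis away from the primary endpoints.** The protocol's curves covered selected AESI only. SAP 4.7 also names time to discontinuation, but no section had planned a time-to-event analysis of AE discontinuation.
- **That PBO-SEP and SEP-SEP cannot be compared.** Distortion between them needs different follow-up. The documents give neither the split of the 64 nor dropout or exposure by column. The exposure categories largely follow the visit days and are not evidence of a difference. No comparison is planned (SAP 7.6, 8.4).
- **That the understatement is several-fold.** Such figures require every subject to stop at the same early time. Ordinary dropout gives the smaller range above.

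**Conclusion.** The point holds in a limited form. The AE tables contain no measure that allows for unequal follow-up. For AEs, SAEs and AE discontinuations that follows the protocol; for selected AESI it results from SAP 4.7, and sample size is a weak reason because the estimate remains feasible at N = 64.

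The percentages are not wrong as observed on-treatment proportions. They are low if read as 12-month risk: by about 10% of the true risk at 20% dropout and about 41% at 70% under constant hazards, but only about 4-7% at 40-60% dropout if all events come in the first 2 months. These sizes rest on assumed dropout, assumed event timing and dropout independent of the event. ALL EXT is affected whether or not the columns differ. The addition is a worthwhile, inexpensive improvement, and no planned inference depends on it.

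**What to change.** - Keep the n (%) and event-count tables. Add a footnote that the percentages are observed proportions over the follow-up each subject had, not 12-month risks.
- For any AE, SAE, AE leading to discontinuation and each AESI category, add the number of subjects with a first event per 100 person-years at risk with 95% CI, for PBO-SEP, SEP-SEP and ALL EXT. Time at risk runs from the first OLE dose to the first event or the end of the AE window. State that window by event type: SAP 7.5 uses 7 days after the last dose but exempts SAEs without giving another limit, while Protocol 15.4.3.1 gives 14 days for SAEs.
- In SAP 4.7, reinstate a Kaplan-Meier or cumulative-incidence estimate of time to first hyperprolactinemia-related AESI, at least for ALL EXT. Say which is used and how discontinuation for other reasons is treated. A similar estimate for AE discontinuation would be a new, optional analysis.
- State that person-year rates assume a roughly constant hazard, should be read beside the time-to-event estimate, and are not meant for comparing columns.

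The cost is a few rows per table and one figure, from AE onset and dosing dates already collected. The downside is wide intervals, especially in the two separate columns.

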## 5. PLANNED ANALYSES

The following analyses will be performed for this study:

- Analyses for independent DSMB meetings
- Final Analysis

### 5.1. DATA AND SAFETY MONITORING BOARD

A DSMB SAP and charter, describing the methodology, meeting schedule, and presentation of results as well as access to results will be maintained by another Contract Research Organization (CRO) and SMPA as separate documents. All DSMB analyses will be performed independently by the CRO approximately three times a year.

### 5.2. INTERIM ANALYSIS

There is no interim analysis of efficacy data planned for this study.

## 5.3. FINAL ANALYSIS

All final, planned analyses specified in this SAP will be performed inhouse by SMPA following this SAP, after database lock.

Some minor modifications may be necessary to the planned design of tables, figures, and listings to accommodate data collected during the actual study conduct.

## 6. ANALYSIS POPULATIONS

Agreement and authorization of enrolled subjects included/excluded from the analysis population listed below will be conducted prior to database lock.

Enrolled subjects in SEP380-303 will include all subjects who signed the informed consent form (ICF) of study 380-303.

### 6.1. SAFETY POPULATION

The Safety Population will consist of all subjects who are enrolled and have received at least one dose of study drug during the 52-week open-label extension treatment period. The Safety Population will be used for the long-term safety, tolerability, and efficacy analyses. Subjects will be analyzed according to the following 3 treatment groups:

- PBO-SEP: Subjects whose actual treatment group is Placebo in study SEP380-301 and received SEP-4199 CR in study SEP380-303.
- SEP-SEP: Subjects whose actual treatment group is either SEP-4199 CR 200 mg/day or SEP-4199 CR 400 mg/day in study SEP380-301 and received SEP-4199 CR in study SEP380-303.
- ALL EXT: all subjects received SEP-4199 CR in study SEP380-303.

## 7. GENERAL CONSIDERATIONS

### 7.1. REFERENCE START DATE AND STUDY DAY

Study Day will be calculated from the reference start date and will be used to show the start/stop day of assessments and events.

Reference start date is defined as the date of the first dose of OLE study medication of study SEP380-303 (Day 1 is the Study Day of the first dose of OLE study medication of study SEP380-303).

- If the date of assessment or event is prior to the reference start date, then:  
Study Day = (date of assessment or event - reference start date).
- If the date of assessment or event is on or after the reference start date, then:  
Study Day = (date of assessment or event - reference start date) + 1.

In the situation where the assessment or event date is partial or missing, Study Day and any

Document: SEP380-303 - Statistical Analysis Plan - Final – 25JAN2024.docx

Version Number:  
Version Date:

Final  
25JAN2024

corresponding durations will appear missing in the listings. Partial assessment or event dates will, however, be presented as is in the listings.

## 7.2. BASELINE

Unless otherwise specified, double-blind (DB) Baseline is defined as the last non-missing measurement taken prior to the first dose of study medication of study SEP380-301, including unscheduled assessments. DB Baseline values are essentially the “Baseline” values of study SEP380-301 and will be directly obtained from the SEP380-301 ADaM datasets.

Open-label (OL) Baseline is defined as the last non-missing measurement taken prior to the first dose of OLE study medication of study SEP380-303, including unscheduled assessments. These values will be derived in SEP380-303 ADaM datasets using data collected in studies SEP380-301 and SEP380-303.

Whenever available, the time information should be accounted for in the derivation of OL Baseline values. In the case where time is not available and the date of the last non-missing measurement and the date of the first dose of OLE study medication coincide, that measurement will be considered the OL Baseline.

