**Table 1: Mapping of study visits to analysis visits.**

Study Visit	Analysis Visit Number	Analysis Visit
NA*	0	DB Baseline
Visit 1E	1	OL Baseline
Visit 1EJ#	1.1	OL Day 1
Visit 2E	2	OL Week 2
Visit 3E	3	OL Month 1
Visit 4E	4	OL Month 2
Visit 5E	5	OL Month 3
Visit 6E	6	OL Month 4
Visit 7E	7	OL Month 5
Visit 8E	8	OL Month 6
Visit 9E	9	OL Month 7

Visit 10E	10	OL Month 8
Visit 11E	11	OL Month 9
Visit 12E	12	OL Month 10
Visit 13E	13	OL Month 11
Visit 14E (if representing true EOT visit). For ET visit mapping see Section 7.4	14	OL Month 12
Visit 15E	15	Follow-up

\* Several assessments from that visit are collected in SEP380-301 study. #An extra visit for Japan (Visit 1EJ) on Day 1 that evaluates ECG.

Original study visit collected on the case report forms (CRFs) will be displayed in the listings.

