## 18.3. ECG EVALUATIONS

Data from the centrally over-read ECG (Electrocardiogram) results will be included in the reporting of this study.

The following ECG parameters will be reported for this study:

- PR Interval (msec)
- RR Interval (msec)
- QRS Duration (msec)
- QRS Axis (deg)
- QT Interval (msec)
- QTcF Interval (msec) (Fridericia's Correction of QT interval)
- QTcB Interval (msec) (Bazett's Correction of QT interval)

- Heart Rate (bpm)
- Overall assessment of ECG as determined by the central over-read:
  - Normal
  - Abnormal, Insignificant
  - Abnormal, Potentially Significant
  - Abnormal, Significant
  - Exclusion Alert (only given for the Screening visit of core study). In table summaries, the category of "Exclusion Alert" will be combined into the category of "Abnormal, Significant".
  - Not Evaluable
- ECG findings

ECG findings will only be listed. Other ECG data will be summarized in tables as well as presented in listings.

The following summaries will be provided:

- For quantitative measurements: By-visit summary of observed values at DB Baseline, OL Baseline, each scheduled OLE study visit (starting from Visit 2E, Visit 1EJ for Japan subjects), and LOCF; by-visit summary of change from DB Baseline at each scheduled OLE study visit (starting from Visit 1E) and LOCF; by-visit summary of change from OL Baseline at each scheduled post-OL Baseline extension study visit (starting from Visit 2E, Visit 1EJ for Japan subjects) and LOCF.
- For ECG overall assessment results as determined by the central over-read ("Normal", "Abnormal, not Clinically Significant (NCS)", "Abnormal, Clinically Significant (CS)", "Not Evaluable"): By-visit summary of number and percentage of subjects in each category at DB Baseline, OL Baseline, each scheduled OLE study visit (starting from Visit 2E, Visit 1EJ for Japan subjects), and LOCF.
- Shift in ECG overall assessment as determined by the central over-read from DB Baseline to each scheduled OLE study visit (starting from Visit 1E) and LOCF, and shift from OL Baseline to each post-OL Baseline extension study visit (starting from Visit 2E, Visit 1EJ for Japan subjects) and LOCF.
- Number and percentage of subjects who met each of the QTc interval prolongation criteria (see [Section 18.3.1](#)) considering both DB Baseline and OL Baseline. The period of evaluation includes both the OLE treatment period and the OLE follow-up period up to and including 7 days post the last OLE dose, including unscheduled visits.

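### SAP 7.2's same-date baseline rule has no exception for the Japan-only Day 1 ECG, so a missing clock time can turn an ECG classed as post-baseline into the OL Baseline for QTc

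*SAP*

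**What the plan says.** SAP Section 7.2 sets the general rule: "Open-label (OL) Baseline is defined as the last non-missing measurement taken prior to the first dose of OLE study medication". It then gives clock time priority: "Whenever available, the time information should be accounted for in the derivation of OL Baseline values". A fallback follows for missing times. It begins "In the case where time is not available and the date of the last non-missing measurement and the date of the first dose", requires the two dates to coincide, and ends "that measurement will be considered the OL Baseline". It names no visit or parameter as an exception.

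SAP Section 7.1 fixes the calendar: "Day 1 is the Study Day of the first dose of OLE study medication of study SEP380-303". The note to Figure 1 agrees and places Visit 1E on the day before dosing starts.

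The footnote to SAP Table 1 (Section 7.3) adds "An extra visit for Japan (Visit 1EJ) on Day 1 that evaluates ECG". The table maps Visit 1E to OL Baseline and Visit 1EJ to a separate analysis visit, OL Day 1. Section 18.3 reports ECG change from OL Baseline at each post-OL Baseline "extension study visit (starting from Visit 2E, Visit 1EJ for Japan subjects"). Section 7.3 explains post-OL Baseline as meaning after the first extension dose.

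**The concern.** For most assessments the fallback is harmless, because the baseline visit is the day before dosing and nothing is scheduled on the first-dose day. The Japanese ECG is different: Visit 1EJ meets the same-date condition by design. When a time is missing, one ECG is both the reference and the first value the SAP calls post-baseline, and it displaces the Visit 1E ECG.

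SAP Section 18.3.1 uses OL Baseline for the 30 to under 60 msec and the 60 msec or greater QTc increases. It also uses it for the counts of values above 450/470, 480 and 500 msec that were absent at OL Baseline. A prolonged QTc first seen at Visit 1EJ would be classed as already present, so it and later exceedances of the same threshold would not be counted against OL Baseline. The consequence is clearest for Japanese subjects who had placebo in the lead-in study, since Day 1 is their first SEP-4199 dose.

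**Working it through.** No stated figure in the plan bears on this point, so there is none to reproduce. The check applies the Section 7.2 rule to one Japanese subject and then follows the effect on the QTc criteria.

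**Inputs.** The Visit 1E ECG is dated the day before first dose (SAP Figure 1 note). The Visit 1EJ ECG is dated Day 1 (Table 1), the first-dose date (Section 7.1). The case examined is a 1EJ ECG taken after the dose, as the SAP's label implies. Comparing ECG with dose needs both times, so I read the fallback as applying when either is missing.

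**Step 1: which ECG becomes OL Baseline.**

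| Times recorded | OL Baseline under Section 7.2 |
|---|---|
| Both, ECG after dose | Visit 1E |
| ECG time missing | Visit 1EJ |
| Dose time missing | Visit 1EJ |
| Both, ECG before dose | Visit 1EJ, correctly |

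**Step 2: effect on the changes.** Let D be the QTc at Visit 1EJ minus the QTc at Visit 1E, and C the true later change from Visit 1E. When 1EJ is the reference:

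- recorded change at 1EJ = D − D = 0
- recorded later change = C − D

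An increase of C is missed at 30 msec when C − D < 30, that is D > C − 30. It is missed at 60 msec when D > C − 60. For C = 35 the first limit is 35 − 30 = 5 msec. For C = 62 the second is 62 − 60 = 2 msec.

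**Step 3: numbers.** The documents do not give D. Assumed range 0 to 30 msec:

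| D (msec) | C = 35 recorded as | At least 30? | C = 62 recorded as | At least 60? |
|---|---|---|---|---|
| 0 | 35 | yes | 62 | yes |
| 5 | 30 | yes | 57 | no |
| 10 | 25 | no | 52 | no |
| 15 | 20 | no | 47 | no |
| 20 | 15 | no | 42 | no |
| 30 | 5 | no | 32 | no |

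From D = 5 on, the second subject is not lost altogether but moves from the 60 msec category to the 30 to under 60 msec category. If D is negative, C − D exceeds C and later increases are overstated.

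**Step 4: scale.** SAP Section 4.4 reports 64 subjects enrolled. If all are in the Safety Population, one reclassified subject moves an ALL EXT percentage by 1/64 = 1.6 points. The number of Japanese subjects and the frequency of missing times are not stated.

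**Step 5: after the change.** If an untimed 1EJ ECG cannot be the baseline, the reference in the first three rows of Step 1 is Visit 1E, the 1EJ change equals D, and later changes equal C.

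**The case against.** The best defence is that the SAP already shows which ECG is meant. Table 1 labels Visit 1E as OL Baseline, Section 18.3 treats 1EJ as post-baseline, and the protocol (Section 7.1) carries baseline values over from lead-in Visit 6. On this view the fallback only settles ties among values already accepted as pre-dose. That shows the intent but does not repair the rule, because the fallback exists for cases where pre-dose status cannot be established. The SAP does write specific rules where it wants them: Section 18.6.1 bars a C-SSRS rating made after the first extension dose from serving as OL Baseline, and Section 18.1 has a tie-break for adverse events on the first-dose day. ECG has neither.

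Other parts of the defence stand and limit the point:

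- **Missing times may be rare.** Section 15 refers to a CRF field for dosing start time, and ECGs go to a central vendor (Protocol Appendix I). With both times present, a post-dose 1EJ ECG is never the baseline.
- **Post-dose timing is not documented.** The supplied protocol does not describe Visit 1EJ. Its position after the dose rests only on the SAP's label and the explanation in Section 7.3.
- **Each QTc criterion in Section 18.3.1 that uses OL Baseline has a DB Baseline counterpart.** DB Baseline comes from the lead-in datasets and cannot be altered by this rule. Observed values by visit and full listings are also planned.

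A reader might infer that a 1EJ ECG documented as pre-dose also biases the results. It does not: Section 7.2 then picks the correct reference, and the only flaw is a redundant OL Day 1 row with zero change.

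A reader might also infer that QTc-based discontinuation or dose-increase decisions are affected. The documents do not support that. The protocol applies those rules at the site during conduct, whereas this is an analysis derivation.

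**Conclusion.** The point holds as a conditional flaw in a stated rule. With the ECG or first-dose time missing, Section 7.2 makes the Visit 1EJ ECG the OL Baseline, against Table 1 and Section 18.3. Per affected subject, later QTc changes from OL Baseline are wrong by D. That matters for increases within D of a 30 or 60 msec limit and for the threshold counts that require absence at OL Baseline.

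It would go too far to say that the Japanese QTc analysis as a whole is biased or that a QT signal would be hidden. Distortion requires a Japanese subject, a missing time, an ECG in fact taken after the dose, and a non-zero Day 1 change. DB Baseline results remain intact. For subjects already on SEP-4199 in the lead-in study, the direction of D is uncertain. The values of D used above are assumptions. The total effect is probably small, and this is a minor point worth settling because it is so easily settled.

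**What to change.** Add to SAP Section 7.2, with a cross-reference in Section 18.3:

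> For ECG, a Visit 1EJ measurement may serve as OL Baseline only if the ECG time and the first OLE dose time are both recorded and the ECG precedes the dose; it is then not also summarised as OL Day 1. If either time is missing, OL Baseline is the last non-missing ECG dated before the first OLE dose (normally Visit 1E, i.e. Visit 6 of SEP380-301).

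Referring to the last ECG dated before the dose, rather than to Visit 1E alone, keeps the unscheduled pre-dose ECGs that Section 7.2 allows. The cost is two sentences of SAP text, a cross-reference and a small programming condition. No new data are needed, and no clinical rule changes.
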